10.1.3. Population of Interest

The exploratory pharmacodynamics analyses will be based on the safety population, unless otherwise specified.

10.1.4. Strategy for Intercurrent (Post-Randomization) Events

A 'While on-study' strategy will be implemented for intercurrent events.

All available data from participants who were withdrawn from the study will be listed and all available planned data will be included in summary tables and figures, unless otherwise specified.

CONFIDENTIAL

208564

10.1.5. Statistical Analyses / Methods

Details of the planned displays are provided in [Appendix 9](#): List of Data Displays and will be based on GSK Data Standards and statistical principles.

Unless otherwise specified, endpoints / variables defined in Section [10.1.1](#) will be summarised using descriptive statistics, graphically presented (where appropriate) and listed.

CONFIDENTIAL

208564

12. APPENDICES

12.1. Appendix 1: Schedule of Activities

12.1.1. Protocol Defined Schedule of Events

Screening Period

Screening Procedure	Screening (up to 30 days prior to Day 1)
Informed Consent	X
Inclusion and Exclusion Criteria	X
Demography	X
Full Physical Exam (incl. weight and height)	X
Medical History and current medical conditions ¹	X
Concomitant Medication Review	X
12 lead ECG in triplicate	X
Vitals (blood pressure, heart rate, body temperature) ²	X
Breath Alcohol Screen	X
Urine Drug Screen	X
HIV, HBV and HCV Screen	X
Tuberculosis (TB) Screening QuantiFERON	X
Haematology/Clinical Chemistry/Urinalysis/Clotting	X
SAE Review	X

1. To include substance usage, family history of premature cardiovascular disease, medication, drug/alcohol history
2. Vital signs are to be taken before blood collection for laboratory tests.

CONFIDENTIAL

208564

Treatment and Follow-Up Period

Procedure	Day -1	Day 1					Day 2	Day 3	Day 5	Day 7	Day 10	Day 14	Day 21	Day 28	Day 42	Day 56	Day 84	Day 126 (follow-up visit)/Early Withdrawal
											±1 day	±1 day	±1 day	±1 day	±2 days	±2 days	±7 days	±7 days
Admission	X																	
In-patient Stay	X		X															
Discharge					X													
Outpatient Visit							X	X	X		X	X	X	X	X	X	X	
Inclusion and Exclusion Criteria	X																	
Breath Alcohol Screen	X																	
Urine Drug Screen	X																	
		Pre-dose	0h	1h	4h	8h	24h											
Dosing ³			X ⁵															
Injection Site Reaction Assessment		X ⁵	X ⁵		X ⁵		X ⁵										X	
Brief Physical Exam	X						X ¹											
Full Physical Exam ⁶																	X	
Haematology/Clinical Chemistry	X	X ²					X ¹	X	X	X	X	X ²	X	X	X	X	X	
Urinalysis	X									X			X			X	X	
12 lead ECG (triplicate)		X								X			X			X	X	
Vitals (blood pressure, heart rate, body temperature) ⁴	X	X		X ¹	X ¹	X ¹	X ¹	X	X	X	X	X	X	X	X	X	X	
PK Sampling		X				X ¹	X ¹	X	X	X	X	X	X	X	X	X	X	
Free & Total OSM Sampling		X				X ¹	X ¹	X	X	X	X	X	X	X	X	X	X	
Immunogenicity Sampling		X										X	X				X	
TPO Sampling		X							X		X					X		
EPO Sampling		X							X		X	X			X			
Concomitant Medication Review			Monitored from screening until end of follow-up visit															
SAE/AE Review			SAEs collected from signing of consent form, AEs collected continuously from time of dose															

CONFIDENTIAL

208564

Footnotes:

1. All post dose time points are in reference to the first injection of IMP.
2. Day 1 Pre-dose sample and Day 21 sample will be fasted for approximately 12 hr and will include lipids
3. IMP administration consists of 3 syringes, all 3 syringes are to be administered as closely together in time as possible
4. Vital signs are to be taken before blood collection for laboratory tests.
5. Assessments should be conducted immediately before first injection (pre-dose) and immediately after last injection (0h). Post dose assessments (4h and 24h) to be conducted in reference to the last injection of IMP. Any injection site reactions to be captured through AE reporting.
6. Full physical exam at follow-up will not include height

- The timing and number of planned study assessments may be altered during the course of the study based on newly available data (e.g., to obtain data closer to the time of peak plasma concentrations) to ensure appropriate monitoring.
- Any changes in the timing or addition of time points for any planned study assessments as the result of emerging pharmacokinetic/pharmacodynamic data from this study must be documented and approved by the relevant study team member and then archived in the sponsor and site study files but will not constitute a protocol amendment. The Competent Authority (CA) and ethics committee (EC) will be informed of any safety issues that constitute a substantial amendment and require alteration of the safety monitoring scheme or amendment of the informed consent form (ICF). The changes will be approved by the CA and the EC before implementation.

12.2. Appendix 2: Assessment Windows

For haematology, chemistry, vital signs, ECG, urinalysis, immunogenicity, PK and biomarker outputs (incl. summaries and figures), Unscheduled and early withdrawal assessments will be included (see [Appendix 4](#): Data Display Standards & Handling Conventions and [Appendix 9](#): List of Data Displays).

Where unscheduled and early withdrawal visits are included in outputs, the following visit slotting will apply. If more than one visit slots to the same analysis timepoint, the closest visit to the analysis timepoint will be included in the summary and figure.

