For PK and PD planned and unplanned assessments will be summarised and listed. PK NCA will use all available data and will use actual relative time, not planned relative time.

For all endpoints an early withdrawal assessment occurred at the time when a planned assessment for that endpoint would have occurred (\pm the visit window), the early withdrawal visit will be slotted to that planned assessment and included in summaries. Where the plots use time as the x-axis, the early withdrawal visit will be included regardless of when the data was collected relative to the study window. For log type data (i.e. AEs), all early withdrawal data will be included in summaries. All early withdrawal data will be listed.

CONFIDENTIAL

208564

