12.4.2. Reporting Standards

General	

 The current GSK Integrated Data Standards Library (IDSL) will be applied for reporting, unless otherwise stated (IDSL Standards Location: https://spope.gsk.com/sites/IDSLLibrary/SitePages/Home.aspx): 
 4.03 to 4.23: General Principles 5.01 to 5.08: Principles Related to Data Listings 6.01 to 6.11: Principles Related to Summary Tables 7.01 to 7.13: Principles Related to Graphics Do not include subject level listings in the main body of the GSK Clinical Study Report. All subject level listings should be located in the modular appendices as ICH or non-ICH listings 	
Formats	

 All data will be reported according to the actual treatment the participant received. GSK IDSL Statistical Principles (5.03 & 6.06.3) for decimal places (DP's) will be adopted for reporting of data based on the raw data collected, unless otherwise stated. Numeric data will be reported at the precision collected on the eCRF. The reported precision from non eCRF sources will follow the IDSL statistical principles but may be adjusted to a clinically interpretable number of DP's. Dates will be reported in the format DDMMCCYY e.g. 01Jan2020 unless otherwise stated. 	
Planned and Actual Time	

 Reporting for tables, figures and formal statistical analyses: 
 Planned time relative to dosing will be used in figures, summaries, statistical analyses and calculation of any derived parameters, unless otherwise stated. 	

CONFIDENTIAL

208564

 The impact of any major deviation from the planned assessment times and/or scheduled visit days on the analyses and interpretation of the results will be assessed as appropriate. Reporting for Data Listings: 
 Planned and actual time relative to study drug dosing will be shown in listings (Refer to IDSL Statistical Principle 5.05.1). Unscheduled or unplanned readings will be presented within the subject's listings. 	
Unscheduled Visits	

 Unscheduled visits will be included in summary tables and figures. Assessment windows for the unscheduled and early withdrawal assessments are specified in Appendix 2: Assessment Windows. All unscheduled visits will be included in listings. 	
Descriptive Summary Statistics	

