12.5. Appendix 5: Derived and Transformed Data

12.5.1. General

Multiple Measurements at One Analysis Time Point

 Where multiple assessments are made, the mean of replicate assessments at any given time point will be used as the value for that time point. This derived mean will be reported in the listing in addition to the individual assessments. If there are two values within a time window, the value closest to the target day for that window will be used. If values are the same distance from the target, then the mean will be taken. Participants having both High and Low values for Normal Ranges at any post-baseline visit for safety parameters will be counted in both the High and Low categories of "Any visit post-baseline" row of related summary tables. This will also be applicable to relevant Potential Clinical Importance summary tables.
Study Day

 Calculated as the number of days from Dose Date: 
 Ref Date = Missing → Study Day = Missing Ref Date < Dose Date → Study Day = Ref Date – Dose Date Ref Date ≥ Dose Date → Study Day = Ref Date – (Dose Date) + 1

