12.9.5. Safety Tables

Safety: Tables					
No.	Population	IDSL / Example Shell	Title	Programming Notes	Deliverable [Priority]
Adverse Events (AEs)					
3.1.	Safety	AE1	Summary of All Adverse Events by System Organ Class and Preferred Term		SAC
3.2.	Safety	AE5A	Summary of Adverse Events by System Organ Class and Preferred Term and Maximum Intensity		SAC
3.3.	Safety	AE1	Summary of Drug-Related Adverse Events by System Organ Class and Preferred Term		SAC
3.4.	Safety	AE15	Summary of Non-serious Adverse Events by System Organ Class and Preferred Term (Number of Subjects and Occurrences)		SAC
Serious and Other Significant Adverse Events					
3.5.	Safety	AE16	Summary of Serious Adverse Events by System Organ Class and Preferred Term (Number of Subjects and Occurrences)		SAC
3.6.	Safety	AE3	Summary of Serious Drug-Related Adverse Events by Overall Frequency		SAC
3.7.	Safety	AE1	Summary of Adverse Events Leading to Permanent Discontinuation of Study Treatment or Withdrawal from Study by System Organ Class and Preferred Term		SAC
Chemistry					
3.8.	Safety	LB1	Summary of Chemistry		SAC
3.9.	Safety	LB17	Summary of Worst-Case Chemistry Results Relative to Potential Clinical Importance (PCI) Criteria Post-Baseline Relative to Baseline		SAC

CONFIDENTIAL

208564

Safety: Tables					
No.	Population	IDSL / Example Shell	Title	Programming Notes	Deliverable [Priority]
3.10.	Safety	SAFE_T1	Summary of Chemistry Results by Maximum CTCAE Grade	Footnote: "CTCAE criteria, V5.0: November 27, 2017"	SAC
Haematology					
3.11.	Safety	LB1	Summary of Haematology	By parameter	SAC
3.12.	Safety	LB16	Summary of Haematology Results by Maximum CTCAE Grade Increase Post-Baseline Relative to Baseline	Footnote: "CTCAE criteria, V5.0: November 27, 2017"	SAC
3.13.	Safety	LB17	Summary of Worst Case Haematology Results Relative to Potential Clinical Importance (PCI) Criteria Post-Baseline Relative to Baseline		SAC
3.14.	Safety	SAFE_T2	Summary of Nadirs for Selected Haematology Parameters	By parameter, treatment group Produce for Platelet count and Haemoglobin. Footnote: "Nadir is the lowest post-baseline value of the parameter"	SAC
3.15.	Safety	SAFE_T3	Summary of Days to Nadir of Selected Haematology Parameters	by parameter, treatment group. Produce for Platelet count and Haemoglobin. Footnote: "Nadir is the lowest post-baseline value of the parameter"	SAC

CONFIDENTIAL

208564

Safety: Tables					
No.	Population	IDSL / Example Shell	Title	Programming Notes	Deliverable [Priority]
Urinalysis					

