12.9.6. Safety Figures

Safety: Figures					
No.	Population	IDSL / Example Shell	Title	Programming Notes	Deliverable [Priority]
Haematology					
3.1.	Safety	SAFE_F1	Subject Profiles for Haematology by Treatment Group	
By Haematology parameter.
 
This output should be produced for:
 
Platelet Count, Haemoglobin
 
Use rules for CTCAE boundaries
 
X axis use 'Actual Relative Time (Days)' from dose. Show all observed values including unscheduled.
 
Add footnote "Figure displays a subset of haematology parameters"
 
Panel by treatment group
	SAC
3.2.	Safety	SAFE_F2	Mean Profile for Haematology by Treatment Group	
By Haematology parameter.
 
This output should be produced for:
 
Platelet Count, Haemoglobin
 
X axis shows visits with approximate temporal spacing
 
Add footnote "Figure displays a subset of haematology parameters"
	SAC
3.3.	Safety	SAFE_F3	LFT Patient Profiles	
ALT = Alanine Amino Transferase, AST = Aspartate Amino Transferase, Alk. Phos. = Alkaline Phosphatase, Total Bili. = Total Bilirubin
	SAC
ECG					
3.4.	Safety	EG7	Empirical Distribution Function for Maximum Change from baseline in QTcF Interval	Both treatments in one plot. Calculate maximum change from baseline.	SAC

CONFIDENTIAL

208564

Safety: Figures					
No.	Population	IDSL / Example Shell	Title	Programming Notes	Deliverable [Priority]
3.5.	Safety	EG8	Distribution of QTcF Change by Visit and Treatment	Use the 0, 30, 60 thresholds following shell.	SAC

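### The SAP does not exempt its maximum-grade and worst-case safety tables from the one-visit-per-window and averaging rules, so an abnormal unscheduled or repeat value can be lost from them

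*SAP*

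**What the plan says.** SAP Section 12.2 brings unscheduled and early-withdrawal assessments into the haematology, chemistry, vital-sign and urinalysis outputs (among others), summaries and figures alike, and then selects: "If more than one visit slots to the same analysis timepoint, the closest visit to the analysis timepoint will be included in the summary". Section 12.5.1, a general derivation rule, keeps the value nearest the target day in each window and adds "If values are the same distance from the target, then the mean will be taken". It also says "the mean of replicate assessments at any given time point will be used as the value for that time point", without limiting this to planned triplicates. Section 12.4.2 states "Unscheduled visits will be included in summary tables and figures" and refers to the Appendix 2 windows for how this is done. The last window ends at Day 133.

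Section 12.9.5 lists seven tables that report a maximum or a worst case:

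- chemistry: 3.9 (PCI) and 3.10 (maximum CTCAE grade);
- haematology: 3.12, titled "Summary of Haematology Results by Maximum CTCAE Grade Increase Post-Baseline Relative to Baseline", and 3.13 (PCI);
- urinalysis: 3.16;
- vital signs: 3.21 and 3.22.

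No programming note for these tables says that every record is used. Nor do the three shells supplied in Appendix 10 (SAFE_T1 for 3.10, SAFE_T4 for 3.16, SAFE_T5 for 3.22). Elsewhere the SAP does write all-data instructions. For Figure 3.1 it says "Show all observed values including unscheduled", and for the non-compartmental analysis "PK NCA will use all available data and will use actual relative time, not planned relative time".

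**The concern.** A rule that keeps one value per window suits a by-visit mean. Applied before a maximum is taken, it can remove the very value that the table exists to show.

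Such values are foreseeable. Protocol Section 7.1.4 requires at least weekly counts below its platelet and haemoglobin thresholds. Section 7.1.1 calls for a repeat sample if a Grade 3 result may be spurious, and Section 8 allows unscheduled safety samples. Section 8.2.4 lets monitoring run past the last scheduled visit. After Day 28 the scheduled visits are 14 to 42 days apart, so an unscheduled draw may be the only information in between.

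Tables 3.10, 3.12, 3.16, 3.21 and 3.22 bear on primary endpoints: CTCAE-graded laboratory results, urinalysis findings, and vital signs of potential clinical importance. Tables 3.9 and 3.13 are supporting PCI displays. With seven participants planned on active treatment, one misclassified participant is 1/7, about 14% of that arm.

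**Working it through.** The plan gives no figure to reproduce. The check applies the written rules to the calendar and then to assumed values.

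**Inputs.** Windows and target days are from SAP Section 12.2.1. Visit tolerances are from the Schedule of Activities: none to Day 7; 1 day for Days 10, 14, 21 and 28; 2 days for Days 42 and 56; 7 days for Days 84 and 126.

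**Rule.** If the scheduled visit took place within tolerance, its distance from target is at most the tolerance. An unscheduled draw is therefore certain to be dropped when |draw day − target day| > tolerance. On the remaining days the result depends on when the visit actually took place.

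Haematology and chemistry:

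| Target | Window | Tolerance | Days dropped / days in window |
|---|---|---|---|
| 2 | 2 | 0 | 0/1 |
| 3 | 3–4 | 0 | 1/2 |
| 5 | 5–6 | 0 | 1/2 |
| 7 | 7–8 | 0 | 1/2 |
| 10 | 9–12 | 1 | 1/4 |
| 14 | 13–17 | 1 | 2/5 |
| 21 | 18–24 | 1 | 4/7 |
| 28 | 25–34 | 1 | 7/10 |
| 42 | 35–49 | 2 | 10/15 |
| 56 | 50–63 | 2 | 9/14 |
| 84 | 64–105 | 7 | 27/42 |
| 126 | 106–133 | 7 | 13/28 |

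Sum: 76/132 = 57.6% of days.

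Urinalysis (targets 7, 21, 84 and 126; windows 2–14, 15–42, 43–105 and 106–133; tolerances 0, 1, 7 and 7): 12/13 + 25/28 + 48/63 + 13/28 gives 98/132 = 74.2% of days.

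**Assumed values, rules applied literally.**

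1. Dropped value, grade lowered. Haemoglobin is 84 g/L on Day 28, 79 on a Day 35 re-check and 85 on Day 42. Day 35 falls in the Day 42 window, 7 days from target, while the visit is at most 2 days away. The 79 is dropped and Grade 3 (below 80) appears as Grade 2.
2. Averaged repeat, grade lowered. Platelets are 46, with a same-day repeat of 58 (×10⁹/L). (46 + 58)/2 = 52, so Grade 3 (below 50) appears as Grade 2. In general a first value x below 50 leaves the Grade 3 range once the repeat reaches 100 − x.
3. Dropped value, primary count changed. ALT is above ULN on an unscheduled Day 70 draw and normal at every other visit. Day 70 is 14 days from the Day 84 target, and the visit is at most 7 days away. The value is dropped and the participant leaves the Grade 1 or higher count in Table 3.10.

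Examples 1 and 2 do not alter the Grade 1 or higher count. Averaging applies only to numeric results. The categorical urinalysis results in Table 3.16 can be dropped but not averaged.

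**The case against.** The strongest reply is that a table of maximum or worst-case results plainly means the worst of everything observed. The supplied shells have no visit dimension to which a per-timepoint rule could attach. SAFE_T1 notes that grading is on the laboratory test value. Section 12.5.1 also has participants with both high and low values at any post-baseline visit counted in both categories, including in PCI tables. The note on Figure 3.1 is a plotting instruction, so its absence from a table proves little. And if the nadir definition in Section 4.2.1 (the lowest post-baseline value) is taken to mean all values, maximum grade deserves the same reading. These points favour the ordinary all-data reading. They do not settle it, because none says whether the maximum is taken before or after one value per window has been selected, and the selection rule is written for these outputs.

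Three further points stand in full. Tables 3.9, 3.12, 3.13 and 3.21 use standard shells that are not supplied and may already use every record; examples 1 and 2 concern Table 3.12. The listings keep all values, as does Figure 3.1 for platelets and haemoglobin. And 59 of the 76 days fall after Day 34, whereas platelet recovery in the earlier single-dose study was evident between Days 28 and 35; haemoglobin took longer.

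A reader might infer more than the documents support:

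- *Almost every unscheduled value is lost*, because "Planned time relative to dosing will be used in figures, summaries, statistical analyses and calculation of any derived parameters, unless otherwise stated" would put each scheduled visit at distance zero. That would nearly nullify the statement in the same section that unscheduled visits enter the summaries, and an unscheduled draw has no planned time.
- *A draw has a 58% chance of being lost.* The figure counts calendar days and says nothing about when draws occur or whether they are abnormal.
- *A Grade 3 count has been hidden.* SAP Sections 2.1 and 2.5 report that a temporary-hold criterion was met, but not which one.

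**Conclusion.** The gap is real and limited. The rules as written reach all seven tables, and no text exempts them. Followed literally, they can understate a maximum grade or PCI category, and they leave values after Day 133 without a place. The exposure is 76 of 132 days for haematology and chemistry and 98 of 132 for urinalysis, assuming that scheduled visits are attended within tolerance and that the window rule is applied before the maximum. The primary count of Grade 1 or higher laboratory results moves only when the lost value was the participant's sole abnormal one. The patient values used above are assumed. Whether the programs behind the four standard-shell tables follow the literal rule cannot be determined from the documents.

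**What to change.** Add one paragraph to SAP Sections 12.2 and 12.5.1. Window selection, and the averaging of ties and unplanned repeats, apply only to by-visit summaries and mean profiles. Maximum-grade, worst-case, PCI and nadir displays (including time to nadir) use every individual post-dose value, scheduled or unscheduled, including those after Day 133. Planned triplicates are still averaged.

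The downside is that a spurious value would count. Keep grading on the laboratory value alone, as Section 12.7.1 already states, and identify any value not confirmed on repeat sampling by a footnote or a listing flag.

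The cost is that paragraph and a check of the source records for seven tables. If the programs already use every record, the paragraph only documents what they do.

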12.2.1. Definitions of Assessment Windows for Analyses

Analysis Set / Domain	Analysis Window		Analysis Timepoint
	Beginning Timepoint	Ending Timepoint	
Haematology and Chemistry	Days less than 0		Screening
	Day 1	Day 1	Day 1
	Day 2	Day 2	Day 2
	Day 3	Day 4	Day 3
	Day 5	Day 6	Day 5
	Day 7	Day 8	Day 7
	Day 9	Day 12	Day 10
	Day 13	Day 17	Day 14
	Day 18	Day 24	Day 21
	Day 25	Day 34	Day 28
	Day 35	Day 49	Day 42
	Day 50	Day 63	Day 56
	Day 64	Day 105	Day 84
	Day 106	Day 133	Day 126

Analysis Set / Domain	Analysis Window		Analysis Timepoint
	Beginning Timepoint	Ending Timepoint	
Vital signs	Days less than 0		Screening
	Day 1 - Pre dose		Day 1 - Pre dose
	Day 1 - 1H		Day 1 - 1H
	Day 1 - 4H		Day 1 - 4H
	Day 1 - 8H		Day 1 - 8H
	Day 2	Day 2	Day 2
	Day 3	Day 4	Day 3
	Day 5	Day 6	Day 5
	Day 7	Day 8	Day 7
	Day 9	Day 12	Day 10
	Day 13	Day 17	Day 14

CONFIDENTIAL

208564

Analysis Set / Domain	Analysis Window		Analysis Timepoint
	Beginning Timepoint	Ending Timepoint	
	Day 18	Day 24	Day 21
	Day 25	Day 34	Day 28
	Day 35	Day 49	Day 42
	Day 50	Day 63	Day 56
	Day 64	Day 105	Day 84
	Day 106	Day 133	Day 126

Analysis Set / Domain	Analysis Window		Analysis Timepoint
	Beginning Timepoint	Ending Timepoint	
ECG and Urinalysis	Days less than 0		Screening
	Day 1	Day 1	Day 1
	Day 2	Day 14	Day 7
	Day 15	Day 42	Day 21
	Day 43	Day 105	Day 84
	Day 106	Day 133	Day 126

Analysis Set / Domain	Analysis Window		Analysis Timepoint
	Beginning Timepoint	Ending Timepoint	
PK/ Free and Total OSM	Day 1 - Pre dose		Day 1 - Pre dose
	Day 1 - 8H		Day 1 - 8H
	Day 2	Day 2	Day 2
	Day 3	Day 4	Day 3
	Day 5	Day 6	Day 5
	Day 7	Day 8	Day 7
	Day 9	Day 12	Day 10
	Day 13	Day 17	Day 14
	Day 18	Day 24	Day 21
	Day 25	Day 34	Day 28
	Day 35	Day 49	Day 42
	Day 50	Day 63	Day 56
	Day 64	Day 105	Day 84
	Day 106	Day 133	Day 126

Analysis Set / Domain		Analysis Window		Analysis Timepoint
		Beginning Timepoint	Ending Timepoint	
Biomarker samples (EPO/ TPO)	EPO	Day 1	Day 1	Day 1
		Day 2	Day 9	Day 7

CONFIDENTIAL

208564

Analysis Set / Domain		Analysis Window		Analysis Timepoint
		Beginning Timepoint	Ending Timepoint	
		Day 10	Day 17	Day 14
		Day 18	Day 34	Day 21
		Day 35	Day 133	Day 56
TPO	Day 1	Day 1	Day 1	Day 1
	Day 2	Day 7	Day 5	
	Day 8	Day 17	Day 10	
	Day 18	Day 34	Day 21	
	Day 35	Day 133	Day 86	

Analysis Set / Domain	Analysis Window		Analysis Timepoint
	Beginning Timepoint	Ending Timepoint	
Immunogenicity	Day 1	Day 1	Day 1
	Day 10	Day 21	Day 14
	Day 22	Day 56	Day 28
	Day 56	Day 133	Day 126

For PK and PD planned and unplanned assessments will be summarised and listed. PK NCA will use all available data and will use actual relative time, not planned relative time.

For all endpoints an early withdrawal assessment occurred at the time when a planned assessment for that endpoint would have occurred (\pm the visit window), the early withdrawal visit will be slotted to that planned assessment and included in summaries. Where the plots use time as the x-axis, the early withdrawal visit will be included regardless of when the data was collected relative to the study window. For log type data (i.e. AEs), all early withdrawal data will be included in summaries. All early withdrawal data will be listed.

CONFIDENTIAL

208564

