4.4. Scientific Rationale for Study Design

The proposed 450 mg single SC dose in Japanese participants is anticipated to result in exposure comparable to the 6 mg/kg (average 417 mg, range 375-443 mg) single SC dose tested in Caucasian participants in the FTIH study 201246 allowing a comparative assessment of ethnic sensitivity in terms of safety, tolerability and PK and PD in a Japanese population. Furthermore, a dose of 450 mg SC aligns with the highest anticipated dose to be administered in the global clinical studies with GSK2330811.

In addition, this study will be conducted in healthy male participants for the following reasons:

- Patients with inflammatory and fibrotic diseases may have existing comorbidities or be taking concomitant medications that may confound the analysis.
- It is anticipated that patients would derive little or no benefit from a single dose of GSK2330811, but that taking part in the study might interfere with their ability to receive other potentially efficacious therapies.
- Animal reproductive toxicity studies have not yet been carried out with GSK2330811 and therefore the benefit-risk of enrolling women of child-bearing

potential in this study, where they are unlikely to derive any direct benefit from a single dose of GSK2330811, does not support their inclusion. Moreover, enrolling only male participants will facilitate comparison with data from study 201246, a single-dose FTIH study of GSK2330811 in predominantly male Caucasian participants [Reid, 2018].

This study will include a placebo arm to ensure that the treatment-attribution of adverse events (AEs) is appropriately blinded and to provide control data for the PD and safety laboratory assessments.

The duration of follow-up will be about 126 days, which will be approximately 5 half-lives of GSK2330811 (half-life of between 19 to 25 days) [GlaxoSmithKline Document Number 2016N284919_02, 2019].

Exploratory endpoints have been chosen to confirm target engagement and further investigate PK/PD relationships in the blood.

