12.6. Appendix 6: Reporting Standards for Missing Data

12.6.1. Premature Withdrawals

Element	Reporting Detail
General	
 Participant study completion (i.e. as specified in the protocol) was defined as completion of all assessment on Day 126. A maximum of 4 non-evaluable participants will be replaced. All available data from participants who were withdrawn from the study will be listed and all available planned data will be included in summary tables and figures, unless otherwise specified. Withdrawal visits will be slotted as per Appendix 2: Assessment Windows or will be summarised as withdrawal visits.

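### The SAP gives inconsistent rules for slotting early-withdrawal samples, and its wide late windows can report a drug or antibody sample under a nominal visit weeks from when it was taken

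*SAP*

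**What the plan says.** Four places in the SAP bear on where an early-withdrawal sample is reported.

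- **Section 12.2 (Appendix 2), opening text.** Unscheduled and early-withdrawal assessments are included in the immunogenicity, PK and biomarker outputs, among others: "Where unscheduled and early withdrawal visits are included in outputs, the following visit slotting will apply". If several visits fall in one window, the closest to the timepoint is used. Section 12.4.2 refers to the same windows.
- **Section 12.2.1, tables.** The PK and OSM windows run without a gap from Day 2 to Day 133. Days 64 to 105 go to Day 84 and Days 106 to 133 go to Day 126. For antibodies, Days 22 to 56 go to Day 28, and the next row is "Day 56 Day 133 Day 126".
- **Section 12.2.1, text after the tables.** Planned and unplanned PK and PD assessments are to be summarised and listed. A conditional rule follows: "For all endpoints an early withdrawal assessment occurred at the time when a planned assessment for that endpoint would have occurred", give or take the visit window, then "the early withdrawal visit will be slotted to that planned assessment and included in summaries". Plots with a time axis include the early-withdrawal visit whenever it occurred, and all such data are listed.
- **Section 12.6.1.** Withdrawal visits are slotted by Appendix 2 "or will be summarised as withdrawal visits".

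The visit windows in the Schedule of Activities (Protocol 1.3) are 2 days either side at Day 56 and 7 days either side at Days 84 and 126. Protocol 4.4 gives a "half-life of between 19 to 25 days".

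**The concern.** The tables give every late sample a home. The text after them gives a home to an early-withdrawal sample taken close to a planned assessment. Section 12.6.1 leaves the choice open. Nothing says which governs, so two programmers could produce different by-visit tables from the same data.

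The tables are the most permissive of the three. A participant who leaves on Day 58 and gives the early-withdrawal antibody sample is counted in the Day 126 row of Table 3.23, whose denominator is the participants with immunogenicity data at that visit. That overstates by 68 days (126 − 58) how long he was observed for antibody formation, which is a secondary endpoint. A drug concentration from Day 64 enters the Day 84 mean in Table 4.1 and is plotted at planned time in Figures 4.2 and 4.3.

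Day 56 is a defect on any reading, because an antibody sample from that day belongs to both Day 28 and Day 126.

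**Working it through.** **Inputs.** Half-life 19 to 25 days and follow-up of about 126 days (Protocol 4.4); analysis windows (SAP 12.2.1); visit windows (Protocol 1.3); 7 participants planned on active drug (Protocol 4.2); predicted Cmax 33 µg/mL at 64.2 kg (Protocol 4.5, Table 1); drug assay LLQ 100 ng/mL (SAP 12.9.7).

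**1. The plan's own figure.** Protocol 4.4 describes follow-up as about five half-lives. 126 / 25 = 5.04 and 126 / 19 = 6.63, so the figure reproduces at the 25-day end. The documents give no fold difference for the windows; those below are derived.

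**2. Do the rules give different answers?** Take an early-withdrawal PK sample on Day 64.
- Tables: Days 64 to 105, so Day 84.
- Text after the tables, reading the visit window as that of the Schedule of Activities: Day 56 ± 2 is Days 54 to 58 and Day 84 ± 7 is Days 77 to 91. Day 64 is in neither, so the slotting condition is not met.
- Section 12.6.1: Day 84, or a separate withdrawal visit.

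**3. Size for drug concentration.** Assuming log-linear terminal decline, fold = 2^(days between actual and nominal day / half-life).

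| Sample and reported day | Days apart | Half-life 25 d | Half-life 19 d |
|---|---|---|---|
| Visit-window edge, Day 84 or 126 | 7 | 1.21 | 1.29 |
| Day 64 as Day 84, or Day 106 as Day 126 | 20 early | 1.74 | 2.07 |
| Day 105 as Day 84 | 21 late | 1.79 | 2.15 |
| Antibody sample, Day 57 as Day 126 | 69 early | 6.77 | 12.39 |

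An early sample is higher than nominal by the fold shown and a late one is lower by it. Day 57 is used for antibodies because Day 56 is the doubly assigned day.

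**4. Effect on a visit mean.** Six participants at the nominal level (set to 1) and one 20 days early: (6 + 1.74) / 7 = 1.106 and (6 + 2.07) / 7 = 1.153, an increase of about 11 to 15%. One 21 days late: (6 + 1/1.79) / 7 = 0.937 and (6 + 1/2.15) / 7 = 0.924, a decrease of about 6 to 8%.

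**5. Would the difference be measurable?** Assuming decline from 33 µg/mL at Day 7 (an assumed Tmax), the Day 126 level is 33 × 2^(−119/19) = 0.43 to 33 × 2^(−119/25) = 1.22 µg/mL. Both exceed the LLQ of 0.1 µg/mL, so imputing low values to zero would not hide it.

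**6. Antibody observation time.** Day 58 is 57 days after dosing: 57 / 25 = 2.3 to 57 / 19 = 3.0 half-lives. Day 126 is 125 days after dosing: 5.0 to 6.6 half-lives.

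**The case against.** The strongest reply is that the rules are ambiguous rather than opposed, and that little depends on them. Much of this stands.

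- A reader might infer that the text after the tables forbids slotting outside the visit window. It does not say so: it provides for slotting inside the window and is silent on summaries outside it. The visit window is also undefined there and could mean the analysis windows. But those are contiguous for PK and OSM, so on that reading the condition would exclude almost nothing. The condition covers early-withdrawal visits alone, and the same text says unplanned PK and PD samples will be summarised.
- A reader might infer false-negative antibody results at Day 126. The 7- to 12-fold figure is a drug ratio. Its effect on detection depends on assay drug tolerance, which the documents do not give. The overstated observation time does not depend on this.
- A reader might infer that late means are always inflated and the terminal phase flattened. The Day 84 window also admits samples 21 days late, and raising the Day 84 mean alone would steepen the Day 84 to 126 segment.
- The drug ratios do not transfer to OSM.
- Withdrawal is expected to be uncommon (Protocol 7.2), the closest-visit rule protects a participant who also has the scheduled sample, and Section 12.4.2 says the impact of major timing deviations will be assessed as appropriate. There is no hypothesis test.

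These points limit the size of the problem. They do not supply a precedence rule or resolve the double assignment of Day 56.

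**Conclusion.** The inconsistency is real and should be corrected, as a moderate point about by-visit reporting. The displays exposed are Tables 3.23, 4.1 and 6.1 to 6.4, and Figures 4.2, 4.3, 6.2, 6.3 and 7.1.

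At the window edge, the mislabelled drug concentration differs from nominal by 1.7- to 2.2-fold, in either direction at Day 84. At Day 126 the late edge equals the visit window, so the excess there can only be on the early side. These are worst cases, resting on log-linear decline and the protocol's half-life range. The effect on a mean assumes one such participant among 7. For antibodies, the supported statement is that the label overstates the observation time.

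A reader might take this as a threat to the PK parameters or to the count of participants with antibodies. It is not. Non-compartmental analysis uses actual times (SAP 9.1.1.2 and 12.2.1), individual concentration plots use actual time, and a participant with a confirmed positive sample remains positive whichever row it sits in.

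**What to change.** State one slotting rule and its precedence, and align Sections 12.2, 12.2.1, 12.4.2 and 12.6.1 with it.

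- For PK, OSM and antibodies, slot an early-withdrawal sample to a nominal visit only within the Schedule of Activities window: Days 77 to 91 (84 ± 7) for Day 84 where that visit is scheduled, and Days 119 to 133 (126 ± 7) for Day 126.
- Extend this explicitly to unscheduled samples. That means amending the opening sentence of the text after the tables in Section 12.2.1, which now has unplanned PK and PD assessments summarised.
- List all other samples, plot them at actual time and keep drug concentrations in the non-compartmental analysis. Show off-window early-withdrawal antibody results in a separate row of Table 3.23, which Section 12.6.1 already permits.
- Remove the Day 56 overlap from the antibody windows.

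The cost is a SAP edit and the matching programming. The downside is that an off-window sample drops out of the by-visit mean, for example leaving 6 of 7 active participants at that visit. No data are lost from listings, actual-time plots or the non-compartmental analysis.
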